7.3 Disposition of Subjects

The reason for screen failure will be summarized based on all screened subjects.

Disposition of all subjects from the safety set will be summarized by vaccine received, overall, and additionally by baseline seropositivity status (seropositive for at least 1 dengue serotype/seronegative for all dengue serotypes). A sample is considered seropositive if the reciprocal neutralizing titer ≥ 10 . Disposition categories will include:

- Completed study
- Did not complete study
- Primary reason for discontinuation from study

A subject is assumed to be ongoing unless he/she completed the end of study CRF, indicating either completion or early termination. The primary reason for study discontinuation will be summarized.

Number of subjects randomized but not vaccinated, in the safety set, full analysis set, per-protocol set, and cell-mediated immunity subset will also be presented. Additionally, the number of subjects will be presented by site and dengue screening IgG status for the safety set.

7.4 Demographic and Baseline Characteristics

Demographic and baseline characteristics will include age, gender, ethnicity, race, weight, height, BMI (calculated based on weight and height measurements at baseline), baseline seropositivity status, and baseline seropositivity status for each dengue serotype. These demographic and baseline characteristics will be summarized descriptively by vaccine received based on the safety set and PPS.

In addition, the demographic and baseline characteristics will also be summarized by baseline seropositivity status (seropositive for at least 1 dengue serotype/seronegative for all dengue serotypes).

Demographic characteristics of screen failure subjects will be summarized.

Summary statistics (number of subjects [n], mean, median, SD, minimum, and maximum) will be generated for continuous variables (age, height, weight, and BMI), and the number and percentage of subjects within each category will be presented for categorical variables (gender, ethnicity, race, and baseline seropositivity).

7.5 Medical History and Concurrent Medical Conditions

Medical history and concurrent medical conditions will be coded using the Medical Dictionary for Regulatory Activities (MedDRA, Version 16.1, or higher) coding system. Concurrent medical conditions are conditions that are recorded as ongoing at screening.

Medical history and concurrent medical conditions will be summarized by SOC, PT, and vaccine received based on the safety set.

7.6 Medication History, Vaccination History, Concomitant Medications, and Concomitant Vaccinations

Medication history, vaccination history, concomitant medications, and concomitant vaccinations will be coded using the World Health Organization DRUG dictionary (WHO Drug Version March 2013 or higher). Medication history (prior medications), vaccination history, concomitant medications, and concomitant vaccinations will be summarized separately by Anatomical Therapeutic Chemical class level 2, preferred medication name, and vaccine received based on the safety set.

A prior medication or vaccine is any medication or vaccine taken before study vaccination (i.e. intake was stopped before study vaccination). A concomitant medication or vaccine is any medication or vaccine ongoing at the time of study vaccination or taken on or after study vaccination.

7.7 Study Vaccination and Follow-Up

The duration of follow-up after study vaccination will be summarized as a continuous variable, and also in categories using the following intervals: 1–30 days, 31–180 days, 181–365 days, and >365 days, by vaccine received based on the safety set. The duration of follow-up is defined as the number of days since vaccination to end of the study.

7.8 Efficacy Analyses

Not applicable.

7.9 Pharmacokinetic/Pharmacodynamic Analysis

Not applicable.

7.10 Other Outcomes

7.10.1 Primary Immunogenicity Analyses

The primary immunogenicity endpoints of the study are GMTs of neutralizing antibodies for each of the four dengue serotypes at post-vaccination visits and seropositivity rates (% of subjects) for each of the four dengue serotypes at post-vaccination visits, where seropositivity is defined as a reciprocal neutralizing titer ≥ 10 .

Both endpoints are derived from dengue microneutralization test (MNT) results. All subjects will undergo blood sampling for neutralizing antibodies measurement at Days 1, 15, 30 (Month 1), 90 (Month 3), 180 (Month 6), and 365 (Month 12).

The number of subjects with non-missing assessment, geometric mean, median, associated 2-sided 95% confidence interval (CI) and associated geometric SD, minimum and maximum will be presented for neutralizing antibody titers for each dengue serotype by vaccine received and visit. Geometric mean titers will be calculated, for each relevant time point as anti-logarithm of $\sum(\log \text{transformed titer}/n)$, where n is the number of subjects with titer information. The 95% CI for GMT will be calculated as the anti-log transformation of upper and lower limits for a two-sided CI of the mean of the log-transformed titers (based on student's t-distribution).

A value of 5 (midpoint between 0 and the lower limit of detection) will be used for Dengue neutralizing antibody titers which are below the lower limit of detection (10). If a reported value is between the lower limit of detection and the lower limit of quantification (differs between serotypes) this value will be replaced with the mid-point between the two.

Geometric mean titers will be plotted over visit, by vaccine received and serotype. In addition, reverse cumulative distribution curves will be plotted by vaccine received, serotype, and visit. These plots will be provided overall and by baseline seropositivity status (seropositive for at least 1 dengue serotype/seronegative for all dengue serotypes) based on the PPS.

Seropositivity rates along with exact 2-sided 95% CI, will be presented for each dengue serotype by vaccine received and visit for each dengue serotype. The exact 2-sided 95% CI of seropositivity rate will be calculated based on Clopper-Pearson method [4]. Seropositivity rates by vaccine received and visit will also be graphically presented by dengue serotype, for at least trivalent, and for tetravalent seropositivity using bar graphs including the percentage of subjects seropositive and corresponding 95% CIs.

Primary immunogenicity analyses will be summarized by vaccine received based on the PPS. A supportive analysis will be provided using the FAS.

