5.1.2 Secondary Objectives

Safety

- To assess the safety of HD-TDV and TDV by treatment arm and baseline dengue seropositivity (MNT).

Immunogenicity

- To assess the post-vaccination neutralizing antibody response against each dengue serotype by treatment arm and baseline dengue seropositivity (MNT).

Vaccine viremia

- To assess vaccine viremia post-vaccination by treatment arm and baseline dengue seropositivity (MNT).

Note: Baseline dengue seropositivity (MNT) is defined as a reciprocal neutralizing titer ≥ 10 for one or more dengue serotype at baseline.

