7.10.2 Secondary Immunogenicity Analyses

The primary immunogenicity analyses will be repeated by baseline seropositivity status (seropositive for at least 1 dengue serotype/seronegative for all dengue serotypes) for the PPS. In addition, the percent of subjects with monovalent (seropositive for only one of the four dengue serotypes), bivalent (seropositive for any two of the four dengue serotypes), trivalent (seropositive for any three of the four dengue serotypes), and tetravalent (seropositive for all four

dengue serotypes) seropositivity, as well as at least bivalent (seropositive for ≥ 2 dengue serotypes) and at least trivalent (seropositive for ≥ 3 dengue serotypes) seropositivity will be summarized by vaccine received and by baseline seropositivity status at each visit for the PPS.

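### Where subjects had dengue antibody before vaccination, the seropositivity rate mixes Day 1 antibody with vaccine response and dilutes differences between the formulations

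*SAP*

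**What the plan says.** SAP 7.10.1 makes the seropositivity rate a primary endpoint beside the GMT, "where seropositivity is defined as a reciprocal neutralizing titer ≥ 10". The planned summary reads: "Seropositivity rates along with exact 2-sided 95% CI, will be presented for each dengue serotype by vaccine received and visit". The cut-off is absolute and does not refer to the subject's own Day 1 titer.

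The same cut-off defines baseline status. Protocol 5.1.2 says: "Baseline dengue seropositivity (MNT) is defined as a reciprocal neutralizing titer ≥ 10 for one or more dengue serotype at baseline". SAP 7.10.2 uses that subject-level status for the stratified analysis: the primary analyses "will be repeated by baseline seropositivity status (seropositive for at least 1 dengue serotype/seronegative for all dengue serotypes) for the PPS".

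SAP 7.4 also tabulates "baseline seropositivity status for each dengue serotype", by vaccine received and additionally by baseline serostatus. It is a baseline characteristic only; nothing in 7.10.1 or 7.10.2 links it to the post-vaccination rates.

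The primary objective (Protocol 5.1.1) concerns the antibody response after vaccination to each serotype. Protocol 4.2 gives the purpose as comparing the two formulations in both dengue-naive and previously exposed subjects, and Singapore was chosen so that both kinds could be enrolled. Both arms receive an active formulation (Protocol 6.1).

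**The concern.** A subject who is at or above 10 to a serotype on Day 1, and stays there, counts as seropositive at every later visit whatever the vaccine does. The trial enrols such subjects on purpose and has no placebo arm to show what the rate would be without vaccination.

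The split in SAP 7.10.2 removes the problem in one stratum only. Subjects seronegative to all four serotypes start below 10 throughout, so their later seropositivity is seroconversion by construction. The other stratum needs only one positive serotype. For any given serotype it can therefore contain both subjects who were already positive to it and subjects who were not. The bivalent, trivalent and tetravalent rates inherit the mixture.

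At stake is how the rate can be read in exposed subjects, one of the two populations that the trial was set up to study. Analyses are descriptive (SAP 7.1), so no type I error or stated power is affected. The cost is to interpretation.

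**Working it through.** The documents state no expected rate, effect size or power, so there is no figure of the plan's own to reproduce. The check is algebra over assumed ranges.

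**Inputs from the documents**
- Cut-off of 10 both at baseline and after vaccination (Protocol 5.1.2; SAP 7.10.1).
- 400 subjects, 200 per arm (Protocol 2.0).
- Day 1 titers taken in all subjects (SAP 7.10.1).

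**Assumptions not in the documents**
- *q*, the share already at 10 or above to the serotype on Day 1, is the same in both arms and runs from 30% to 90%.
- Baseline positives stay positive.
- Response rates *r* among subjects below 10 on Day 1 are 60% in one arm and 80% in the other.
- 100 baseline-seropositive subjects per arm.

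**Formulas**
- Planned rate in an arm: S = q + (1 − q) r.
- Difference between arms: S2 − S1 = (1 − q)(r2 − r1).

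**Baseline-seropositive stratum.** The power columns are for a two-sided 5% comparison of two proportions. They are a yardstick only, since no test is planned. The last column restricts the comparison to subjects below 10 to the serotype on Day 1, of whom there are 100(1 − q) per arm.

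| q | S1 | S2 | Difference | Power, rate as planned | Power, Day 1 negatives only (n per arm) |
|---|---|---|---|---|---|
| 30% | 72% | 86% | 14 points | 68% | 74% (70) |
| 50% | 80% | 90% | 10 points | 51% | 59% (50) |
| 70% | 88% | 94% | 6 points | 32% | 39% (30) |
| 90% | 96% | 98% | 2 points | 13% | 16% (10) |

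With 60 to 140 subjects per arm instead of 100, power for the rate as planned is 33% to 65% at q = 50% and 9% to 16% at q = 90%.

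**Floor.** With r = 0 the formula gives S = q. A vaccine with no effect would show 50% seropositive at q = 50% (Clopper-Pearson 95% CI 40% to 60%, n = 100) and 90% at q = 90% (82% to 95%).

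**Pooled primary analysis, 200 per arm.** Let a share e of subjects be baseline-seropositive, with the same r in all subjects below 10. The multiplier is then 1 − e·q.
- e = 30%, q = 50%: 1 − 0.15 = 0.85, so 20 points become 17 (yardstick power 98%).
- e = 70%, q = 90%: 1 − 0.63 = 0.37, so 20 points become 7.4 (yardstick power 66%).

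**The case against.** The strongest reply is that the comparison in exposed subjects does not rest on this rate. SAP 7.10.1 says: "The primary immunogenicity endpoints of the study are GMTs of neutralizing antibodies for each of the four dengue serotypes at post-vaccination visits". GMTs are repeated by baseline serostatus, reverse cumulative curves are drawn by serostatus, and neither has a ceiling at 10. With 100 subjects per arm, a two-fold GMT ratio would be seen with yardstick power of about 100%, 94% or 76% at an assumed log10 SD of 0.4, 0.6 or 0.8. This stands. GMTs and curves are still post-dose cross-sections that carry Day 1 antibody, so they do not measure within-subject change.

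A second reply is that a vaccine with no effect would be visible, because the baseline rate per serotype is tabulated. This also stands. If positives stay positive, r can be recovered as (S − q)/(1 − q): with q = 80%, rates of 92% and 96% return 12/20 = 60% and 16/20 = 80%. What is missing is the direct estimate and its confidence interval, without the assumption that no baseline positive falls below 10.

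A reader might go further and infer that in exposed subjects the endpoint neither measures response nor separates the formulations. The documents do not support that. It is approached only as q nears 100%, and they give no serotype-specific prevalence. One positive serotype is enough to enter the stratum, so q for another serotype may be low. At q of 50% or less, half or more of the difference survives.

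Nor is dilution the same as bias between arms: allocation is 1:1 and stratified by screening IgG. Finally, the rate is the protocol's own endpoint, so the change is an addition to it and not the correction of an error.

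**Conclusion.** The point holds as one of interpretability. In the pooled analysis and in the stratum seropositive to at least one serotype, the serotype-specific rate has a floor at the baseline prevalence q, and differences between formulations are multiplied by (1 − q). For 20 points in that stratum this leaves 14 to 2 points over q = 30% to 90%. These sizes assume that baseline positives stay positive and that q is equal in the two arms. The values of q are illustrative, and the true loss could lie anywhere in the range or outside it.

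The all-seronegative stratum is free of the problem, and the mitigation already planned is real. No readable planned analysis conditions on the subject's own Day 1 titer to the serotype. SAP 7.10.4 is redacted and cannot be checked. The addition is worth making because it is cheap and serves the stated aim in exposed subjects.

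**What to change.** Keep the pooled seropositivity rate as the protocol-defined endpoint. In SAP 7.10.1 and 7.10.2 add, for each serotype, visit and vaccine received:

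- (a) the proportion reaching a titer of at least 10 among subjects below 10 to that serotype on Day 1, with a Clopper-Pearson 95% CI;
- (b) the geometric mean fold rise from Day 1, with 95% CI, among subjects at 10 or above to that serotype on Day 1.

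Both are needed: where baseline prevalence is high, (a) rests on few subjects (about 10 per arm at q = 90% with 100 exposed per arm) and (b) covers the rest.

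The cost is SAP wording and more tables, with small denominators for (a) in places. No new sample or visit is needed. The benefit is mainly a clear estimate of response. The gain in power to separate the formulations is modest, for example from 51% to 59% at q = 50%.

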7.10.2 Secondary Immunogenicity Analyses

The primary immunogenicity analyses will be repeated by baseline seropositivity status (seropositive for at least 1 dengue serotype/seronegative for all dengue serotypes) for the PPS. In addition, the percent of subjects with monovalent (seropositive for only one of the four dengue serotypes), bivalent (seropositive for any two of the four dengue serotypes), trivalent (seropositive for any three of the four dengue serotypes), and tetravalent (seropositive for all four

dengue serotypes) seropositivity, as well as at least bivalent (seropositive for ≥ 2 dengue serotypes) and at least trivalent (seropositive for ≥ 3 dengue serotypes) seropositivity will be summarized by vaccine received and by baseline seropositivity status at each visit for the PPS.

7.10.3 Vaccine Viremia Analysis

Vaccine Viremia is defined as a positive result from the Dengue Vaccine Screening Reverse Transcription-Polymerase Chain Reaction (RT-PCR).

The vaccine viremia endpoints of the study are the vaccine RNA level, incidence, and duration, of vaccine viremia for each of the four TDV strains (TDV-1, TDV-2, TDV-3, TDV-4) post-vaccination.

Vaccine viremia will be assessed on blood samples collected pre-vaccination on Day 1 (Month 0) and post-vaccination on Days 5, 7, 9, 11, 15, 17, 21 and 30 (Month 1).

Vaccine viremia summaries will be presented by vaccine received and visit, overall and by baseline seropositivity status (seropositive for at least 1 dengue serotype/seronegative for all dengue serotypes) based on the Safety Set.

The number of subjects with non-missing assessment, mean, associated 2-sided 95% confidence interval (CI) and associated SD, median, minimum, and maximum will be presented for vaccine RNA (vRNA) levels (expressed as \log_{10} [genome equivalents per mL]) measured by RT-PCR for each TDV strain.

Incidence rates of vaccine viremia along with exact 2-sided 95% CI, will be presented for each TDV strain. The exact 2-sided 95% CI of incidence rate will be calculated based on the Clopper-Pearson method.

The duration of vaccine viremia for each serotype = visit date when vaccine viremia is last detected (positive result) – visit date when vaccine viremia is first detected (positive result) + 1 day. For the number of subjects with non-missing assessment, mean, associated 2-sided 95% confidence interval (CI) (based on student's t-distribution) and associated SD, median, minimum, and maximum will be presented. The number and percentage of subjects with different categories of vaccine viremia duration will also be presented. In addition, the number of days to onset of viremia will be summarized descriptively and categorized for TDV strain.

Samples that are positive in the Dengue Vaccine Screening RT-PCR will undergo the Vaccine Confirmation Sequencing assay to determine the nucleotide at three attenuation loci sites.

Summaries for each TDV strain will include the following categories: No loci with possible reversion, 1 locus with possible reversion, 2 loci with possible reversion, and all loci with possible reversion.

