13.1.1 Analysis Sets

Safety Set: The Safety Set will consist of all randomized subjects who received the trial vaccine.

Full Analysis Set (FAS): The FAS will consist of all randomized subjects who received the trial vaccination and for whom a valid a pre-dose and at least one valid post-dose blood sample is taken.

Per-Protocol Set (PPS): The PPS will consist of subjects in the FAS who have no major protocol violations. The major protocol violation criteria will be defined as part of the blinded data review prior to the unblinding of subject's treatment assignment. The categories of major protocol violations include: (1) not meeting selected entry criteria, (2) receiving wrong trial treatment (3) receiving prohibited therapies, and (4) other major protocol violations that may be identified during blinded data reviews.

The primary analysis of immunogenicity and vaccine viremia endpoints will be based on the PPS; other supportive analysis may be provided for the FAS. The safety analysis will be based on the Safety Set.

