7.2.1 Protocol Deviations

The criteria described in [Table 7.a](#) will be used to identify subjects who will be excluded from the PPS and will be identified prior to database lock and unblinding. These criteria are considered to have a potentially significant impact on the immunogenicity, and also vaccine viremia results of the subject. Subjects excluded from PPS due to receiving incorrect vaccine will be identified after unblinding. Reasons for exclusion of subjects from the analysis sets will be summarized based on the Randomized Set.

Table 7.a Criteria for Exclusion from the PPS

Criteria for Exclusion	Probable Method of Identification
Not receiving the study vaccine administration ^(a)	Identified programmatically using “End of Study Drug” page question “Did the subject complete the study vaccine?” and/or dosing data
Not having a valid pre-dose and at least 1 valid post-dose measurement for dengue neutralizing antibodies ^(b)	Identified programmatically using immunogenicity data
Not receiving the assigned vaccine, except for the 250 subjects whose vaccines were transposed because two packaging campaigns assigned incorrect vaccine lots, which was identified on 16Oct2015.	Identified after unblinding (e.g. subject who was randomized to TDV but received HD-TDV, subject who was randomized to HD-TDV but received TDV)
Product preparation error	Identified through protocol deviation log
Subject meets inclusion criterion 5 or any of exclusion criteria 1, 2a, 2c, 2d, 3, 4, 5 or 6 (subject to blinded medical review)	Subjects identified programmatically using CRF-recorded data. Subjects will be identified before unblinding, and a blinded review list sent for clinical science review to determine evaluability status for each identified subject. Note that exclusion criteria 2d and 3 identify subjects’ use of prohibited medications prior to enrollment.
Use of prohibited medications at study start (subject to blinded medical review)	Potential prohibited medications (Appendix C) to be identified by sending a blinded review list of CRF-recorded medication data for medical review to determine evaluability status for each identified subject.

(a) Subjects with this protocol violation will be excluded from the Safety Set, and thus also from the FAS and the PPS.

(b) Subjects with this protocol violation will be excluded from the FAS, and thus also from the PPS.

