Measurements for dengue neutralizing antibodies and viremia collected outside the windows as specified below will be excluded from the respective visits in the Per-Protocol analysis:

- Dengue neutralizing antibodies: $D15 \pm 5$ days, $D30 \pm 5$ days, $D90 \pm 15$ days, $D180 \pm 15$ days, $D365 \pm 15$ days
- Viremia: $D5 \pm 1$ day, $D7 \pm 1$ day, $D9 \pm 1$ day, $D11 \pm 1$ day, $D15 \pm 1$ day, $D17 \pm 1$ day, $D21 \pm 2$ days, $D30 \pm 5$ days

Other significant deviations may be identified based on blinded data reviews of deviation logs throughout the study, subject to medical review.

In addition, all significant protocol deviations identified based on the deviation logs will be summarized based on the safety set.

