7.13.2 Summary of Changes

This section describes major changes to the SAP Version 1.0, dated 07 September 2016.

Final Version	Section	Description of Change.
2.0	General	The main rationale for this amended SAP was the Protocol Version 3.0, dated 25 April 2017 where the planned interim analysis including data up to Day 180 (Month 6) was removed. Other sections were updated for clarification and harmonization across the Dengue program.
	1.1	Administrative updates and use of eSignatures.
	5.3	Deletion of “(all subjects)” from the exploratory endpoint regarding humoral immune response for consistency to other endpoints.
	7.1.2	Imputation rules for missing severity and missing relationship to study drug were added for AEs for consistency across the Dengue program.
	7.2	The Randomized Set was introduced.
	7.2.1	Table 7.b was updated. Removal of the exclusion of single measurements as only subjects can be excluded from the Per-Protocol Set. Measurements outside of windows will not be included in the respective Per-Protocol analysis. Removal of criterion “Inadvertent unblinding of subject’s vaccine assignment to relevant site personnel and study team” as such a criterion is more relevant for pharma studies. As we have blood sample assessments for vaccine studies there is no bias here for the immunogenicity analysis results.

7.6	Clarification was added for definition of prior/concomitant medications/vaccinations.
7.10.1	Plots for seropositivity rates were added.
7.10.3	Details were added for summary of nucleotides at attenuation loci's.
7.10.5	Details added for analysis of humoral immune response data.
7.10.6	Details added for analysis of CMI data.
7.11.1	Handling of prolonged solicited AEs was added.
7.12	Update of Interim Analysis Section as no interim analysis will be conducted for this trial.
8.0	Reference Section was updated to capture all references mentioned in the SAP.

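### Vaccine viremia: the protocol makes the PPS the primary analysis set, but SAP 7.10.3 uses the Safety Set without declaring the departure, so the PPS criteria and viremia windows of SAP 7.2.1 are not applied to viremia

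*SAP*

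**What the plan says.** The protocol is explicit. Section 13.1.1 reads "The primary analysis of immunogenicity and vaccine viremia endpoints will be based on the PPS; other supportive analysis may be provided for the FAS", and the synopsis in Section 2.0 has the same rule. Both places assign the Safety Set to the safety analysis.

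SAP 7.1 states that it builds on protocol Version 3.0, which carries that rule. For antibody titers it follows the rule: "Primary immunogenicity analyses will be summarized by vaccine received based on the PPS" (SAP 7.10.1). For viremia, SAP 7.10.3 presents the summaries by vaccine received and visit, both unsplit and by baseline serostatus, and the sentence closes with "seropositive for at least 1 dengue serotype/seronegative for all dengue serotypes) based on the Safety Set".

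SAP 7.2.1 treats viremia as a per-protocol outcome. Of the PPS exclusion criteria it says "These criteria are considered to have a potentially significant impact on the immunogenicity, and also vaccine viremia results of the subject". It then lists viremia windows for eight visits, Day 5 to Day 30, under the rule "Measurements for dengue neutralizing antibodies and viremia collected outside the windows as specified below will be excluded from the respective visits in the Per-Protocol analysis". The change summary in SAP 7.13.2 repeats the link: "Measurements outside of windows will not be included in the respective Per-Protocol analysis".

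**The concern.** Someone programming from the SAP cannot satisfy both sections. Section 7.2.1 supplies exclusion criteria and windows for a per-protocol viremia analysis. Section 7.10.3, where that analysis should be specified, names only the Safety Set.

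Three things are at stake.

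- **Population.** Viremia is a named secondary objective, and Protocol 6.2 gives the higher frequency of TDV-2 viremia as one of two observations behind the reduced TDV-2 content. Under 7.10.3 the viremia tables would include subjects whom Table 7.a removes from the antibody tables, for example those with a product preparation error or a disqualifying immune-altering therapy. The two sets of results would then be read against each other on different populations.
- **Timing.** By-visit incidence and RNA level would carry no stated rule for samples taken off schedule.
- **Traceability.** A departure from the protocol's stated primary population should be declared and justified, and this one is not.

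**Working it through.** No formula applies: the point concerns the analysis set, and the trial states no power or sample-size calculation to reproduce. The check is a comparison of the relevant sections.

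| Place | Set or rule for viremia |
|---|---|
| Protocol 2.0 and 13.1.1 | PPS primary; FAS possible as support |
| SAP 7.2.1, Table 7.a | PPS criteria said to matter for viremia results |
| SAP 7.2.1, windows | Eight viremia windows, tied to the Per-Protocol analysis |
| SAP 7.10.3 | Safety Set; no PPS or FAS version named |
| SAP 7.10.4 | Redacted, cannot be checked |
| SAP 7.11.1 | Viremia used only as a subgroup factor for adverse events, on the Safety Set |

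**Is the move explained elsewhere?**

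1. SAP 7.13 declares one change of set: summaries that were to cover all randomized subjects now use the Safety Set. Viremia was not among those, since the protocol had placed it on the PPS.
2. The SAP 7.13.2 entry for Section 7.10.3 mentions only the attenuation-loci summary.
3. The packaging-error text in SAP 7.2 does not move viremia either. It answers the error with an adapted PPS that keeps the 250 affected subjects and analyses by vaccine received, plus an FAS sensitivity analysis.

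**Which viremia summaries do the windows concern?** The post-vaccination visits are Days 5, 7, 9, 11, 15, 17, 21 and 30. The gaps are 2, 2, 2, 4, 2, 4 and 9 days, which sum to 25. Four of the seven gaps are 2 days, covering 4 × 2 = 8 of the 25 days. At those visits a sample taken 2 days late falls on the next visit's scheduled day. The ±1-day window of 7.2.1 would exclude it from the visit's table; 7.10.3 has no such rule. This is a property of the schedule and says nothing about how often it happens.

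Duration differs. SAP 7.10.3 defines it as date of last positive − date of first positive + 1 day, using actual visit dates, so a nominal-visit window is not needed. As an illustration, suppose a subject is positive only on Day 9 and at the Day 11 visit taken 2 days late, on Day 13. The duration is 13 − 9 + 1 = 5 days. Dropping the Day 13 sample as out of window would give 9 − 9 + 1 = 1 day. Similarly, if a subject's only positive sample is out of window, excluding it would remove the subject from overall incidence.

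**Serostatus split.** The Safety Set in SAP 7.2 does not require a valid pre-dose sample. A vaccinated subject without a baseline MNT result belongs to it but cannot be placed in either serostatus group that 7.10.3 asks for. The PPS avoids this, because Table 7.a requires a valid pre-dose titer.

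**The case against.** The strongest case on the other side has five parts.

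- **A Safety Set analysis is defensible.** Viremia bears on safety: 7.10.3 includes possible reversion at attenuation loci, and 7.11.1 uses viremia as a subgroup for adverse events on the Safety Set. This stands as a reason to keep a Safety Set analysis. It is not a justification the SAP gives, and it does not explain windows tied to a per-protocol analysis.
- **The largest known deviation does not separate the sets.** The 250 transposed subjects are in the Safety Set and, absent another violation, in the PPS, and both sets are analysed by vaccine received. This stands. The remaining difference is mainly preparation errors, missing valid titers, and entry or medication violations, most of them subject to blinded review. It may be small.
- **A reader might infer that the PPS criteria are never used, or that no per-protocol viremia analysis will be run.** The documents do not support either. The PPS governs the antibody, humoral and cell-mediated analyses (SAP 7.10.1, 7.10.2, 7.10.5, 7.10.6). Section 7.2.1 presupposes a per-protocol viremia analysis, and 7.10.4 cannot be read. What can be said is that the visible text plans none.
- **SAP 7.13.2 is a log of changes between SAP versions.** If Version 1.0, which is not available here, already used the Safety Set, no entry was due there. This stands for 7.13.2. The opening statement of 7.13 is where the departure belonged.
- **Applying the windows to every viremia endpoint could discard true positives.** This stands and limits the fix.

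**Conclusion.** The protocol and SAP disagree on the primary analysis set for viremia, the visible SAP does not declare or justify the difference, and SAP 7.2.1 and 7.10.3 do not fit together. As written, the PPS criteria and the viremia windows are not applied to viremia.

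The effect on the estimates cannot be sized. The documents give no count of subjects removed by Table 7.a or of samples outside the windows. A reader might infer that the viremia results will be biased, or that the comparison between formulations will be distorted. Nothing in the documents shows that, and it is not claimed. The window question concerns the by-visit incidence and RNA-level tables; duration already runs on actual dates.

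The matter is of moderate weight: a secondary endpoint, in a trial with no hypothesis tests, but an undeclared departure from the stated primary population that is cheap to put right. The conclusion assumes that the redacted Section 7.10.4 holds no PPS viremia analysis. If it does, what remains is to say so in 7.10.3.

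**What to change.** In SAP 7.10.3:

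1. Name the PPS as the primary set for viremia, as the protocol states.
2. Apply the 7.2.1 viremia windows to the by-visit incidence and RNA-level tables only.
3. State that overall incidence, days to onset and duration use all samples at their actual dates.
4. Repeat the summaries on the Safety Set as supportive analysis, and say how subjects without a baseline MNT result are handled in the serostatus split.

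If the Safety Set was intended as primary, declare and justify that in SAP 7.13, still provide the PPS analysis, and state whether the windows apply to the Safety Set tables.

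Either route costs a few lines of SAP wording and a second run of the same tables. No new data are needed.
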